## Outcomes and baseline characteristics

**Outcome measures.** Outcomes in this trial are reflected below in Table 1. The primary outcomes for this trial are the Strengths and Difficulties Questionnaire (SDQ) total problem score, and the Overreactivity subscale of the Parenting Scale. An additional primary outcome relating to observed parenting is not addressed in this SAP. Additional outcomes are broadly grouped into parenting capacity, child outcomes and other parental outcomes. Of note is that at each assessment point, the SDQ was administered in an age-appropriate form (aged 2-3 years, aged 4 and above). Scores are interchangeable between forms of the SDQ and thus these were ‘stacked’ for analysis.

In the original trial protocol, the data analysis plan included Parenting Daily Hassles and Plotkin Child Vignettes. Due to issues with data collection, Parenting Daily Hassles data were not considered to be reliable and thus we dropped this outcome from the analysis plan. Plotkin Child Vignettes data were not collected due to the need to minimise time and frequency of home visits during COVID-19 lockdowns.

**Baseline characteristics.** A number of baseline family characteristics are also relevant to this analysis. These include:

- Child age at baseline
- Parental education (beyond high school vs not)
- Family income (moderate poverty vs no poverty)
- Family structure (single-parent vs other)

We will also consider total child behaviour problems (SDQ total problems score) and parental distress (CESD-10) as relevant baseline characteristics. We will include these baseline characteristics in relevant imputation and effect modification models.

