## Analysis strategy

**Descriptive statistics.** We will describe each study arm using means, standard deviations, proportions and quantiles with respect to key demographics for parents and children.

**Missing data.** It is unlikely that our analysis will accrue more than 10% missingness for any one outcome. However, to ensure that subsets of data can be used in later analyses, we will implement a multiple imputation strategy across all outcomes.

First, we will inspect individual scale responses at each assessment point will be inspected. In situations where participants have answered 75% or more of scales (or subscales where these are analysed separately) scored using simple sums, we will sum the available items and ‘upweight’ these to match the same possible range as for the full scale. This strategy is based on the generally high reliability and validity established for all study measures in this analysis, and is a conservative version of the rule originally proposed by Graham (2012). Where scales do not use simple sums (specifically, AUDIT-C), we will reserve individual items for imputation.

Second, we will specify an imputation model using fully conditional specifications. All scale variables will be analysed using predictive mean matching with five donors. Where items are imputed for AUDIT-C and cannabis use, we will use a conditional imputation model to account for the logic of these items’ scoring and an ordered logit link. We will include as auxiliary variables all relevant baseline characteristics identified above, as well as the site-specific stratum variable. We will undertake 10 imputations separately for each trial arm.

It is likely that the number of variables to be included will be too large for one imputation model. If a single imputation model fails due to nonconvergence or multicollinearity, we will undertake three imputation models using the same set of auxiliary variables in each one:

- SDQ problem subscales (primary outcome) and prosocial behaviour subscale;
- Overreactivity (primary outcome) and parenting capacity outcomes; and
- other parental outcomes.

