Both the Marital Conflict Questionnaire and DAS-7 pertain only to people who reported being partnered at a given assessment point. We will assess any changes in eligibility for these measures over assessment points and use conditional imputation to account for these variables. In addition, because CTSPC-R was only administered to a subset of participants for whom home visits were possible, we will not include CTSPC-R in any imputation models.

**Effect estimation.** The general framework for effect estimation will be generalised linear mixed-effects models, with measurements (level 1) nested within families (level 2). The general form of each model is to include terms at level 1 for categorical time and for the interaction of intervention by categorical time, and at level 2 for study site as the stratification factor. This is equivalent to a model where the baseline measure is constrained to be equal between groups. Consistent with guidance from Coffman et al. (2016), we will not include a level 2 intervention term as this is essentially uninterpretable in the context of randomisation.

For each outcome model, we will select an appropriate outcome distribution, preferring an identity link where possible. If necessary to accommodate distributional violations, we will use percentile-based confidence intervals, undertaking cluster-level bootstrapping within each imputation and pooling runs to generate confidence intervals. In situations where variables have a limited range and discrete values, we will consider use of an ordered logit model. We will use Rubin's rules to combine estimates from multiple imputations.

The test of effectiveness will focus on the six-month value of the outcome. Correspondingly, we will examine the intervention-by-time interaction for the six-month assessment point for each intervention, and undertake a Wald test for each interaction (or, if bootstrapped models are used, examine a 97.5% confidence interval).

**Sensitivity analysis.** We will re-estimate all outcome models using unimputed data.

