### Additional analyses

**Effect modification analyses.** We will explore moderation of intervention effects at the six-month and 12-month assessment point for primary outcomes, child outcomes and the Brief Child Abuse Potential Inventory. To simplify analysis, we will not include post-intervention estimates in these models. Each candidate moderator will be interacted with time and with intervention by time, and a Wald test will be computed on the relevant three-way interaction terms to establish the presence of effect modification. Candidate moderators include study site (given differences in TAU across each site), baseline characteristics described above, and baseline values of child conduct problems (SDQ total problems scale) and of parental distress (CESD-10).

To evaluate the presence of moderation by baseline value of the outcome, we will consider two strategies. The first is to estimate random slope models and compare models with intercept-slope covariances (i.e. with unstructured covariance matrices of random effects) against those without using standard inferential tests. However, this may pose challenges for convergence and interpretation. In the event that it does, we will use time-by-time analyses with an appropriate ANCOVA model with terms for intervention allocation, stratum and baseline value of the outcome as predictors, in addition to candidate moderators. Each candidate moderator will be interacted with intervention status, and a Wald test will be computed on the interaction term to establish the presence of effect modification.

**Mediation analyses.** We will use a fully longitudinal mediation model to explore causal pathways to intervention impacts where a) a plausible relationship exists between the intervention, a mediator and an outcome; b) the effect estimate of the mediator is significant at six months; and c) the effect estimate of the outcome is significant at 12 months (using a  $p < 0.05$  threshold). This model will include paths between intervention allocation, mediator and outcome, and will control for site and for mediator and outcome values at baseline.

Indirect effects will be estimated via percentile-based confidence intervals derived from bootstrapping to account for asymmetries in the confidence interval induced by multiplying two regression terms. Separate indirect treatment effects will be reported for each intervention compared to TAU.

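### The mediation model adjusts the non-randomised mediator-to-outcome path only for site and the two baseline values, leaving out baseline family characteristics the trial already holds

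*SAP*

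**What the plan says.** Under Additional analyses, the SAP states: "We will use a fully longitudinal mediation model to explore causal pathways to intervention impacts". An analysis is run where a plausible relationship exists, the mediator effect is significant at six months and the outcome effect is significant at 12 months. The model "will control for site and for mediator and outcome values at baseline". For inference, "Indirect effects will be estimated via percentile-based confidence intervals derived from bootstrapping".

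Outcomes and baseline characteristics lists child age, parental education, family income and family structure, and adds baseline SDQ total problems and CESD-10. Their use is stated there: "We will include these baseline characteristics in relevant imputation and effect modification models". The effect modification paragraph, just before the mediation paragraph, takes them up: "Candidate moderators include study site (given differences in TAU across each site), baseline characteristics described above". Mediation is not named in either place.

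On missing data, Analysis strategy plans multiple imputation across all outcomes "to ensure that subsets of data can be used in later analyses", with 10 imputations by arm. It expects that a single imputation model may prove too large. If that model fails, three are fitted: SDQ subscales; Overreactivity with parenting capacity; and other parental outcomes. They share only the auxiliary variables.

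**The concern.** Arm is randomised, so its effects on the mediator and on the outcome are protected. The mediator is not randomised. Families with a lower or higher mediator score at six months may differ in poverty, education, family structure or distress, and these may also drive the 12-month outcome. Adjusting for the baseline mediator and outcome removes the part of such a factor already expressed at baseline. It does not remove what the factor goes on to do afterwards.

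The four family characteristics never enter the mediation model. Baseline SDQ total and CESD-10 enter only when one of them is itself the mediator or the outcome.

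At stake is how a reported indirect effect is read. The SAP presents it as a pathway and will report one for each intervention against TAU. A percentile bootstrap interval reflects sampling error and does not show confounding.

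The imputation fallback raises a smaller issue. When mediator and outcome sit in different imputation models, each is imputed without the other's follow-up values, which weakens their estimated association.

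**Working it through.** The SAP gives no effect size, sample size or power for mediation, so there is no figure to reproduce. The checks below show direction and mechanism only.

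**1. Confounding of the mediator-outcome path.**

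From the SAP: six-month mediator M6, 12-month outcome Y12, controls for baseline mediator M0 and baseline outcome Y0 (site is left out of the illustration).

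Assumed, not from the SAP: one family factor C with SD 1 and effect g at each measurement; M0 = gC + error, with total variance 1; Y0 = gC + 0.3·M0 + error (SD 0.9); M6 = −0.3·arm + 0.5·M0 + gC + error (SD 0.8); Y12 = b·M6 + 0.5·Y0 + gC + error (SD 0.8).

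Variance of C left after the SAP's baseline controls:

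v = 1 / [1 + g²/(1 − g²) + g²/0.81]

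Bias in the mediator coefficient when C is omitted:

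bias = g²v / (g²v + 0.64)

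For g = 0.2: v = 1/(1 + 0.0417 + 0.0494) = 0.917; g²v = 0.0367; bias = 0.0367/0.6767 = 0.054.

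| g | v | g²v | bias | estimate if b = 0.20, same sign | estimate if b = 0.20, opposite sign |
|---|---|---|---|---|---|
| 0.1 | 0.978 | 0.0098 | 0.015 | 0.215 | 0.185 |
| 0.2 | 0.917 | 0.0367 | 0.054 | 0.254 | 0.146 |
| 0.3 | 0.826 | 0.0744 | 0.104 | 0.304 | 0.096 |

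The opposite-sign column gives C the effect −g on Y0 and Y12. This leaves v unchanged and reverses the sign of the bias. If C has no effect after baseline on either the mediator or the outcome, the bias is zero. With b = 0 the estimate equals the bias itself, so a path can appear where none exists. Multiplied by the assumed arm effect of −0.3, that gives a spurious indirect effect of about −0.005, −0.016 or −0.031.

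A simulation with n = 400,000 on the same-sign inputs gave 0.015, 0.055 and 0.102 for b = 0, and 0.217, 0.256 and 0.306 for b = 0.20. Adding C to the outcome equation returned 0.00 and 0.20.

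The SAP does not say whether its longitudinal model also includes the six-month outcome. A separate simulation that included it, with b = 0, gave 0.01 to 0.09 for same-sign effects and values down to −0.11 for opposite-sign effects. The bias therefore does not depend on that choice.

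**2. Imputation in separate models.**

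This arises only if the fallback is triggered, the mediation analysis uses those imputed data, the pair crosses models (for example Overreactivity at six months to SDQ at 12 months), and both significance conditions are met.

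Rough limit: if imputed values carry none of the cross-link, the association survives only in families with both values observed. At 10% missing per measure, that is 0.90 if the same families lack both, and 0.90² = 0.81 if missingness is independent. At 5% it is 0.95 and 0.95² = 0.9025.

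Simulations with assumed inputs and values missing completely at random, as a share of the full-data path:

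| Method | 10% missing | 5% missing |
|---|---|---|
| Regression imputation by arm, separate models | 83–91% | 91–95% |
| Five-donor predictive mean matching, separate models | 88–95% | 93–98% |
| The same, with the six-month outcome in the mediation model | 84–100% | 92–99% |

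The SAP specifies matching: "All scale variables will be analysed using predictive mean matching with five donors". When mediator and outcome were imputed in one model, 99–102% of the path was kept. The SAP thinks missingness above 10% for any one outcome unlikely, so the loss is modest and towards the null. Pairs within one imputation model are unaffected.

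**The case against.** The strongest reply is that the plan does not contradict itself. Site and both baseline values form a defensible adjustment set that removes the most direct confounding, and a longer list is partly a matter of judgement. A reader might infer that the SAP recognises the family characteristics as confounders and then forgets them. It does not: it calls them relevant for imputation and effect modification, which says nothing about whether they confound this path. That objection stands. The point is therefore an inexpensive improvement to a model with a causal aim, not an inconsistency.

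A reader might also infer that the SAP has no missing-data plan for mediation. That goes too far. Imputation is planned with later analyses in mind, Rubin's rules are given, and for bootstrapped outcome models the SAP describes "undertaking cluster-level bootstrapping within each imputation and pooling runs to generate confidence intervals". Only an explicit link to mediation is missing, which is a matter of detail.

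Nor would adding covariates close the gap. They remove measured confounding only. In a separate simulation on assumed inputs, covariates capturing half of the confounder's variance left about half of the shift (+11% of an original +20%).

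Finally, mediation is exploratory and runs only after two significance conditions. That limits the importance of the point but does not answer it, because any indirect effect reported will be read as a pathway.

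**Conclusion.** The concern holds in this form: the stated adjustment set leaves the mediator-outcome path open to bias, in either direction, from family factors that keep acting after baseline. It rests on the wording of the mediation paragraph and on the fact that the mediator is not randomised, not on any simulated figure.

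The size for this trial is unknown. A reader might take the tabulated values as estimates of its bias. They are not, because every input is assumed and they range from nil to about half of an assumed path of 0.20 (0.104/0.20 = 52%).

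The imputation point is secondary and conditional. It concerns cross-model pairs under the fallback only, is modest at 10% missingness or less, and weakens pathways without creating false ones.

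The six-month effectiveness tests do not depend on the mediation model and are unaffected. The change should be made, but nothing in the primary analysis turns on it.

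**What to change.** 1. Add child age, parental education, family income, family structure, baseline SDQ total and baseline CESD-10 (the last two where not already the baseline mediator or outcome) to both the mediator and the outcome equation.
2. State that unmeasured mediator-outcome confounding remains possible, and report a simple sensitivity analysis. One option is to vary an assumed correlation between the mediator and outcome errors and report the value at which the indirect effect reaches zero.
3. If the three-model fallback is used and a pair crosses models, impute that pair in one model, by arm, with the same auxiliaries. Keep the SAP's existing rules: AUDIT-C by item, SDQ by subscale. Full-information maximum likelihood is an alternative. State that the significance conditions and the mediation estimate may then rest on different imputed data.

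The cost is SAP wording, a few extra parameters per model using variables already collected, one sensitivity analysis, and one additional imputation run per affected pair. Item-level and subscale imputation make some of those runs larger than a pair of scale totals would suggest.

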**Table 1. Outcome measures**

Measure	Variable	BL	PT	6-mo	12-mo	Analysis strategy
Primary Outcomes						
Strengths and Difficulties Questionnaire (SDQ; 2-4 years; 4-18 years)	Child behavioural problems	X	X	X	X	Sum score
Overreactivity Scale	Parental harsh discipline	X	X	X	X	Sum score
Additional Outcomes						
Parenting capacity						
Composite Caregiving Questionnaire	Self-efficacy Empathy Helplessness Reflective function	X	X	X	X	Subscale scores
Difficulties in Emotion Regulation Scale (DERS-SF)	Emotion regulation	X		X	X	Sum score
Parent Cognition Scale	Parental attributions	X	X	X	X	Sum score
Laxness Scale	Dysfunctional discipline	X	X	X	X	Sum score
Brief Child Abuse Potential Inventory	Child abuse risk	X	X	X	X	Sum score
Child outcomes						
Parent-Child Conflict-Tactics Scale-Revised (CTSPC-R)	Parenting practices				X	Sum score
SDQ Prosocial Behaviour Subscale	Child prosocial behaviour	X	X	X	X	Sum score (of subscale)
Other parental outcomes						
Alcohol Use Disorders Identification Test Consumption (AUDIT-C)	Parental alcohol and substance use	X		X	X	Scale score (complex scoring)
Cannabis use	Parental alcohol and substance use	X		X	X	Single item
Center for Epidemiologic Studies Depression Scale (CESD-10)	Parental mental health	X	X	X	X	Sum score
Generalized Anxiety Disorder (GAD-7)	Parental mental health	X	X	X	X	Sum score

Marital Conflict Questionnaire	Partner conflict	X	X	X	X	Sum score
Dyadic Adjustment Scale (DAS-7)	Partner conflict	X	X	X	X	Sum score
Exploratory outcomes						
SDQ problem behaviour subscales	Child behavioural problems	X	X	X	X	Subscale scores
Other outcomes not in this SAP						
Child and Adolescent Service Use Schedule (CA-SUS)	Health service utilization (children)	X		X	X	
HUI3 proxy parental report and Health Status Classification System Preschool Version	Health-related quality of life (children)	X		X	X	
HUI3	Health-related quality of life (adult)	X		X	X	
Emotional Availability Scale (EAS)	Observed parenting (parental sensitivity)	X	X	X	X	
EAS (child scales)	Responsiveness	X	X	X	X	

BL, baseline; PT, post-treatment

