***Exploratory analyses.*** We will undertake three sets of exploratory analyses: Triple P vs COSP, analyses for the CTSPC-R, and trajectory-based analyses.

***Triple P vs COSP.*** For all outcome models, we will re estimate analyses with COSP as the reference category to estimate

***CTSPC-R.*** Because of COVID-19 restrictions, collection of CTSPC-R data via home visit was severely restricted. Thus, we will analyse this as an exploratory outcome. The CTSPC-R is only collected at the 12-month assessment point. For this outcome, we will estimate a single-level model with terms for intervention arm and study site, using an appropriate outcome distribution and link function.

***Trajectory-based models.*** Given the multiple assessment points in this trial, we will also explore developing trajectory-based estimates of intervention impacts for primary outcomes and child outcomes. After considering the most likely functional form of the time relationship suggested in primary outcome models, we will treat time as continuous and describe the impacts of interventions on outcome trajectories using interaction terms for intervention status by linear or quadratic time trends.

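### The exploratory CTSPC-R model uses no baseline information, giving up precision in an already reduced sample

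*SAP*

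**What the plan says.** The CTSPC-R paragraph under Exploratory analyses (SAP, Additional analyses) gives the timing, "The CTSPC-R is only collected at the 12-month assessment point", and the reason for the shortfall: "collection of CTSPC-R data via home visit was severely restricted", attributed to COVID-19. It sets the status, "Thus, we will analyse this as an exploratory outcome", and the analysis: "we will estimate a single-level model with terms for intervention arm and study site". The outcome distribution and link are left to be chosen.

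Other parts of the SAP bear on the same outcome:

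- **Missing data** (Analysis strategy): "because CTSPC-R was only administered to a subset of participants for whom home visits were possible, we will not include CTSPC-R in any imputation models".
- **Table 1:** CTSPC-R is the only outcome with no baseline measurement. Overreactivity (labelled "Parental harsh discipline"), Laxness, the Brief Child Abuse Potential Inventory, the SDQ and the CESD-10 are all taken at baseline.
- **Baseline characteristics:** child age, education, income, family structure, SDQ total and CESD-10 are listed as relevant, and their use is then defined: "We will include these baseline characteristics in relevant imputation and effect modification models".
- **Effect estimation:** the other outcomes are analysed in a longitudinal model that includes their own baseline value, held equal across arms.

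**The concern.** Every other outcome gains precision from its own baseline through the longitudinal model. CTSPC-R cannot, and nothing replaces it. The SAP uses its listed baseline characteristics in imputation, from which CTSPC-R is excluded, and in effect modification models. Even if the latter cover CTSPC-R (Table 1 groups it with the child outcomes), they test interactions and do not adjust the arm comparison. The one sensitivity analysis, re-estimation on unimputed data, cannot change a result that was never imputed.

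Two things are at stake:

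- **Precision.** The sample is reduced, so information is given up where it is scarcest.
- **Balance.** Whether a family could be visited at 12 months was settled after randomisation. If the kind of family visited differed between arms, the resulting baseline imbalance would stay in the estimate. The SAP plans no comparison of families with and without CTSPC-R that would show it.

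**Working it through.** The SAP gives no sample size, power or precision figure for CTSPC-R, so there is no figure to reproduce. It also gives neither the number of families observed nor any correlation between baseline measures and CTSPC-R. The values of R², r, n and effect size below are assumptions.

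**1. Precision, linear model.** Let R² be the share of CTSPC-R variance, beyond arm and site, explained by the baseline covariates. The ratio of adjusted to unadjusted standard error is √(1 − R²). The equivalent gain in sample size is 1/(1 − R²) − 1.

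| R² (assumed) | SE ratio | SE reduction | Equivalent gain in families |
|---|---|---|---|
| 0.1 | √0.9 = 0.949 | 5% | 1/0.9 − 1 = 11% |
| 0.2 | √0.8 = 0.894 | 11% | 1/0.8 − 1 = 25% |
| 0.3 | √0.7 = 0.837 | 16% | 1/0.7 − 1 = 43% |

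Over a wider range of correlation (R² = r²), the equivalent gain runs from 4% at r = 0.2 (1/0.96 − 1) to 56% at r = 0.6 (1/0.64 − 1).

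**2. Power for one comparison with TAU.** Two-sided 0.05, assumed difference 0.5 SD, residual SD √(1 − r²):

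| Families per arm (assumed) | r = 0 | r = 0.3 | r = 0.5 |
|---|---|---|---|
| 30 | 0.49 | 0.53 | 0.61 |
| 50 | 0.71 | 0.75 | 0.82 |
| 80 | 0.89 | 0.91 | 0.96 |

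**3. Cost of two covariates.** With three arms and four agencies, the planned model has 1 + 2 + 3 = 6 coefficients. At an assumed 30 per arm, residual degrees of freedom fall from 90 − 6 = 84 to 82. That raises the standard error by about √(84/82) − 1 = 1%. The covariates repay this once R² exceeds about 1 − 82/84 = 2.4%.

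**4. Selection into the visited subset.** A simulation of 2,000,000 families with no treatment effect used Y = rX + √(1 − r²)·e, where X is a baseline covariate. The chance of a visit was logistic in X (intercept −0.5), and 38% were observed. The table shows the spurious arm difference in SD units.

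| How visiting depends on X | Model | r = 0.3 | r = 0.5 | r = 0.6 |
|---|---|---|---|---|
| Same in both arms (slope 0.5) | Unadjusted | 0.003 | 0.001 | −0.004 |
| One arm only (slopes 0 and 0.5) | Unadjusted | 0.089 | 0.148 | 0.171 |
| One arm only (slopes 0 and 0.5) | Adjusted for X | 0.001 | 0.002 | −0.003 |

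Selection that operates alike in the arms leaves the contrast essentially unbiased. Selection that differs by arm does not, and adjustment removes the part carried by the measured covariate.

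**The case against.** A reader might infer that the arm-and-site model is valid only if being visited is unrelated to the outcome. The SAP does not support that reading. In the check above, selection on a prognostic variable that worked the same way in both arms produced no material bias; it restricts the population to which the result applies. Bias needs selection that differs by arm. The SAP gives no sign of this: it attributes the shortfall to pandemic restrictions, an external cause, and site is already in the model.

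Further points on the other side:

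- **Arm plus stratification factor is a legitimate randomised comparison.** It also follows the SAP's general form, since no effect-estimation model adjusts for another scale's baseline. This stands: nothing is contradicted. But elsewhere the outcome's own baseline does that work, and here nothing does.
- **The size is assumed.** This stands. At r = 0.2 the gain is only 4% of families. The √(1 − R²) rule also holds only for a linear model; with another link, such as a logit, adjustment can change what the effect measures.
- **Stakes are low.** This stands. The test of effectiveness rests on six-month values, whereas CTSPC-R is measured at 12 months only. Harsh discipline and abuse risk are also covered by Overreactivity, a primary outcome, and the Brief Child Abuse Potential Inventory.
- **Adjustment can bring its own problems.** A long covariate list, or one shortened after seeing the data, would undermine prespecification. The SAP's imputations are run separately by arm and exclude CTSPC-R, so they are a poor source for missing covariate values. Both points shape the fix but do not remove the case for it.

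**Conclusion.** The point holds as a minor loss of efficiency, not as an error that invalidates the analysis. The CTSPC-R model makes no use of closely related baseline measures that the trial already collects, in the one outcome that has no baseline value of its own.

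Under a linear model and an assumed R² of 0.1 to 0.3, adjustment would cut the standard error by 5% to 16%. The true figure cannot be fixed from the SAP. A bias of the order of 0.09 to 0.17 SD would arise only if visiting depended on prognosis in one arm and not the other, as simulated. That is a possibility the plan leaves unexamined, not one it gives evidence for, and adjustment would remove only what the chosen covariates explain.

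Severity is minor because the SAP itself makes the outcome exploratory.

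**What to change.** In the CTSPC-R paragraph, define the single-level model as having terms for arm, site, baseline Overreactivity and baseline Brief Child Abuse Potential Inventory. Fix this set in advance, with no choice that depends on the data. Then add three short statements:

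- Missing values of the two baseline covariates are filled by a simple method blind to arm, such as the overall mean, and not from the arm-specific imputations.
- If a link other than identity is used, the reported effect is stated to be conditional or marginal.
- Baseline measures are tabulated by arm for families with and without CTSPC-R.

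All the variables are already collected. The cost is a few sentences, two degrees of freedom and one extra table.
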